2.2. Secondary objectives

1. To assess the non-invasive strategy as compared to the invasive usual strategy for the management of patients regarding vasopressor-free days at day 28, organ failure progression, fluid balance, and duration of mechanical ventilation support.
2. To assess the impact of the non-invasive strategy on the number of lab tests ordered, the number of vascular punctures performed, the magnitude of related pain reported by the patients, the evolution of blood haemoglobin level, the number of red cell transfusions administered during the ICU stay, the number of catheter-related infections, and on the direct hospital medical costs of care.
3. To determine the efficiency of the non-invasive strategy when compared to the recommended invasive strategy (ICER: 'Cost/Life day gained at 28 days').
4. To evaluate the budget impact of the generalization of the non-invasive strategy (in case of demonstrated non inferiority) in France from the viewpoint of the French health system on a 5 years' time frame

2.3. **Outcome measures**

Primary outcome measure

All-cause mortality by 28 days after randomisation

Secondary outcome measures

- To account for the potential bias brought by deaths occurring as the result of life-sustaining treatments withdrawal/withholding, as frequently encountered in ICUS, we will record such events from inclusion to Day 35 (i.e., until one week after the primary time point)(56)
- Cumulative incidence of death from inclusion through Day 90
- Cumulative survival free of IAC insertion, from inclusion through Day 90
- Number of patients who underwent IAC insertion, in both groups
- Evolution of daily Sequential Organ Failure Assessment (SOFA)(57) score during the first seven days
- Daily amount of intravenous fluid given for rapid vascular volume expansion from Day 1 to Day 7
- Daily fluid balance from Day 1 to Day 7
- Duration of mechanical ventilation
- Ventilator-free days from Day 1 to Day 28 (for this purpose patients dying between randomisation and Day 28 will be assigned a 0 value; for survivors at Day 28, all the days free of invasive mechanical ventilation through an endotracheal tube within the 28-day period will be taken into account)
- Proportion of patients treated by renal-replacement therapy between Day 1 and Day 28

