We will develop a mobile application to automatically estimate arterial blood gas parameters from central venous parameters and SpO₂ (see APPENDIX 2). As the study is not cluster randomized, the mobile app with the arterial blood parameters calculator will be available for all investigators regardless whether they are in charge of patients randomized in the “invasive” (presence of IAC) or the non-invasive group. To minimize this potential source of bias, we want to emphasise, and this will be clearly reminded in the mobile app, that central venous blood drawing will not be allowed in the “invasive” group, except for ScvO₂ measurements.

Modalities of patients' general management

In both group, patients will be managed following international and national guidelines, except for the IAC insertion.

Regarding blood sampling for lab tests, to avoid unnecessary blood spoliation in both arms, we strongly encourage investigators and attending intensivists to properly assess the real need of each lab test ordered. We discourage sampling for routine (daily or more frequent) monitoring or after changes in FiO₂ or PEEP. If blood gas were drawn for suspicion of metabolic or respiratory disorder, only the control after therapeutic intervention will be allowed.

In addition, to decrease blood spoliation during sampling through any vascular catheter (IAC for the invasive group, CVC for the non invasive group), we strongly suggest to apply the following procedure that may help minimizing the discard volume of blood withdrawn before the sampling.(62,63)

After cleaning the catheter hub, draw off 3 mL (for sampling through IAC) or 5 mL (through CVC) of blood (i.e., at least 2 times the catheter's priming volume)(64) with a syringe and waste the syringe. Draw the blood sample through the Vacutainer system. Be sure to sample blood from a line of the catheter not dedicated to continuous vasopressor therapy (to avoid bolus or discontinuous infusion).

4. Study design

The projected study will be a multi-centre, pragmatic, randomised, controlled, open, two-parallel-group, non-inferiority clinical trial with 1:1 assignment of interventions.

Although blinding is not possible due to the nature of the assessed intervention, the primary endpoint is objective (mortality at day 28). The trial will associate medical, surgical, and mixed ICUs, as well as academic tertiary care hospitals and community hospitals.

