4.1. Randomisation

Randomisation will be electronically centralised via a dedicated website.

Randomisation will be stratified on centres, invasive mechanical ventilation (yes or no) and vasopressor dosage, namely < or \geq 0.18 μ g/kg/mn of continuous iv norepinephrine (ie. 0.36 μ g/kg/mn of continuous iv norepinephrine tartrate) or of epinephrine or of the sum of both medications dosages at time of enrolment.

The statistician in charge of the project will determine permutation blocks, the size of which will not be known by the investigators.

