4.7. Measures taken to minimise or avoid bias

Recruitment

All patients admitted in the participating ICUs during the study period will be screened for eligibility. Investigators will make every effort to include all consecutive eligible patients to avoid selection bias. Investigators and study personal at each centre will fill in a screening-log form in which will be recorded included and non included eligible patients' characteristics (age, gender, Simplified Acute Physiology score [SAPS II](67), cause of shock, ICU survival, cause of non inclusion if applicable) to allow assessing the representativeness of the study population and drawing conclusions concerning the generalizability of the results.

Randomisation

Randomisation is mandatory to minimise selection bias.

Stratification

Stratification on centres, invasive mechanical ventilation and vasopressor dosage at time of enrolment is planned to have well balanced groups concerning the general care approach (which could differ between centres).

Definition of safety criteria for IAC insertion in the experimental group

The study scientific committee has set reasonable and consensual safety boundaries that will fix in which circumstances the insertion of an IAC will become an inescapable need. Doing so will contribute to limiting group contamination which would occur if too many patients from the experimental group had an IAC.

Choice of the primary outcome measure

As blinding of investigators and of all ICU staff members is not technically feasible, we chose a "hard" endpoint (Day-28 mortality) to minimise bias.

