6.1. Sample size

In a non-inferiority randomised clinical trial, we usually hypothesize *a priori* an equal incidence of the event of interest in the two groups compared. In the present study, our *a priori* hypothesis is different. Indeed, we expect a marginal benefit of the non-invasive approach, because the systematic IAC insertion may harm the patients through catheter-related infections and through blood spoliation. However, even demonstrating that the non-invasive approach is not inferior to the systematic IAC insertion approach could be considered as a positive result (cf., Risk/benefit ratio section).

We therefore assume that the mortality rate at day 28 will be 22.5% in experimental group and 25% in the control group. We set the non-inferiority margin at 5%, power at 80% and alpha risk at 5%. Such hypotheses led us to plan the inclusion of 1010 patients.

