6.2. Statistical analysis of clinical outcomes

General principles

The statistical analyses will be performed by the INSERM CIC 1415 unit and supervised by [name]. SAS 9.4 and R 3.3 (or further versions) softwares will be used. A detailed analysis plan will be *a priori* defined. Later modifications must occur before unblinding the database. The statistical analysis will be conducted on the per-protocol and intention to treat (ITT) populations as recommended for non inferiority trials. A statistical report will be written in agreement with the standards as specified in the CONSORT Statement and its extension for non pharmacological interventions and for non inferiority trials (<http://www.consort-statement.org/>)

Baseline characteristics

Baseline characteristics will be reported per group using descriptive statistics. No statistical test will be performed.

Groups to be compared

The ITT principle will be applied. Nevertheless, patients who would withdrew consent to study participation will be discarded, as required by the French legislation.

Because patients are ICU patients, it is expected to have no lost-to-follow-up patient. We moreover plan to collect the place of birth, such that we will be able to collect the vital status asking to the city halls. If there are several lost-to follow-up patients, we will use multiple imputation.

The per protocol population will be defined during the blind review.

Statistical analysis of the primary outcome

The between-group difference (experimental group minus usual care group) in rates of day-28 mortality will be estimated based on the 2-sided 95% Confidence Interval (CI). The upper boundary of the 95% CI will be compared with the non inferiority margin of 5%. If non-inferiority is demonstrated, the upper bound of the 95%CI will be compared to 0: if it is lower than 0, then a superiority conclusion will be drawn.(68)

As a sensitivity analysis, we will perform a multivariate logistic regression, to estimate the odds ratio adjusted on the stratification variables.(69)

Statistical analysis of secondary clinical outcomes

- Day-90 mortality: the between-group difference in rates of day-90 mortality will be estimated based on the 2-sided 95% CI.
- Number of patients who underwent IAC insertion, in both groups.

No statistical test will be performed for this outcome, which would be nonsense.

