The primary analysis of the primary outcome will be the determination of the between-group difference (noninvasive group minus invasive group) in rates of day-28 mortality, estimated with a binomial generalized estimating equation (GEE) model with identity link adjusted on the stratification variables and on the center effect (Pedroza 10.1186/s12874-016-0217-0). A switch from noninferiority to superiority is *a priori* planned if the hypothesis of noninferiority with a noninferiority margin of 5 percentage points is verified. These hypotheses will be assessed using the stratified Farrington-Manning test for differences in proportions.

Secondary outcomes analysis

Statistical analyses for secondary outcomes will not be adjusted for multiplicity; therefore, secondary-outcome findings should be interpreted as exploratory.

- Day-90 mortality will be analyzed with the same model as the primary outcome .
- Cumulative incidence of death from randomization through Day 90 will be analyzed with a Cox model.
- ICU mortality and hospital mortality will be analyzed in a competing risks framework. A hazard ratio will be computed from the whole groups using a Fine and Gray regression model. ICU discharge or hospital discharge will be considered as competing events.

The following outcomes will be described with median and quartiles and compared between groups using median differences:

- Duration of ICU stay from randomization to discharge.
- Duration of hospital stay from randomization to discharge.
- Duration of mechanical ventilation from randomization and Day 28.
- Ventilator-free days from randomization to Day 28.
- Renal replacement therapy-free days from randomization to Day 28.
- Vasopressor therapy-free days from randomization to Day 28.

For each outcome, 95% confidence intervals of the median difference will be computed using unstratified bootstrapping (10,000 samples with replacement). Vasopressor therapy-free days, renal replacement therapy-free days and duration of mechanical ventilation do not account for the competing risk of death.

The following outcomes will be represented with boxplots at each day:

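### The primary day-28 risk difference is validly analysed, but it adjusts only for the randomisation factors and leaves recorded prognostic information such as age and cause of shock unused, at a modest cost in precision

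*SAP*

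**What the plan says.** - **Primary model.** The SAP (Primary outcome) specifies a binomial "generalized estimating equation (GEE) model with identity link adjusted on the stratification variables and on the center effect". Non-inferiority at 5 points, and then superiority, are assessed by a stratified Farrington-Manning test.
- **Factors.** Protocol 4.1: "Randomisation will be stratified on centres, invasive mechanical ventilation (yes or no) and vasopressor dosage", with dose below versus at or above 0.18 µg/kg/min.
- **Sensitivity model.** The logistic model in Protocol 6.2 also adjusts only for the stratification variables.
- **Recorded data.** The screening log in Protocol 4.7 covers included and non-included eligible patients and lists "characteristics (age, gender, Simplified Acute Physiology score [SAPS II](67), cause of shock, ICU survival", plus the reason for non-inclusion. Its stated purpose is to assess representativeness.
- **Decision rule in the protocol.** Section 6.2: "The upper boundary of the 95% CI will be compared with the non inferiority margin of 5" per cent.
- **Timing.** The SAP's summary of changes says that the final GEE model, and the decision to use the Farrington-Manning test, were settled during data analysis, after a within-centre correlation of 0.02 had been seen in each group.

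**The concern.** Age, cause of shock and physiological severity can be expected to predict death in shock. Adjusting a marginal risk difference for such baseline variables leaves the quantity estimated and its margin unchanged, reduces its standard error, and corrects for chance imbalance between arms. No planned analysis does this beyond the randomisation factors.

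Precision matters because the sample size has no reserve. The 80% power relies on an assumed 2.5-point benefit, which the protocol itself calls marginal. No allowance is made for patients removed from the analysis after they withdraw or refuse consent.

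**Working it through.** **Inputs from the documents.** The endpoint is binary: "All-cause mortality by 28 days after randomisation" (Protocol 2.3). Protocol 6.1 assumes that the "mortality rate at day 28 will be 22.5% in experimental group and 25% in the control group". It also states: "We set the non-inferiority margin at 5%, power at 80% and alpha risk at 5" per cent. Section 6.2 uses the upper limit of a two-sided 95% interval, which is a one-sided 2.5% test. Section 4 describes a "non-inferiority clinical trial with 1:1 assignment of interventions". Section 6.2 expects no loss to follow-up.

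**Input not in the documents.** R², the share of outcome variance explained by baseline covariates, is an assumption and is shown as a range.

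**Step 1: reproduce the sample size.**
n per arm = (1.96 + 0.8416)² × (0.225×0.775 + 0.25×0.75) / (0.05 + 0.025)² = 7.849 × 0.361875 / 0.005625 = 504.9, so 505 per arm and 1010 in total. This matches. A one-sided 5% level would give 398 per arm (796), which does not.

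**Step 2: precision with no covariates.**
- SE = √(0.361875/505) = 2.677 points. The half-width is 1.96 × 2.677 = 5.25 points.
- Power at −2.5 points = Φ(7.5/2.677 − 1.96) = Φ(0.842) = 80.0%.
- At zero difference (25% in both arms), SE = √(0.375/505) = 2.725 and power = Φ(5/2.725 − 1.96) = Φ(−0.125) = 45.0%.

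**Step 3: gain over the planned adjustment.** Covariates multiply the SE by √(1 − R²). The fair comparator is the planned model, not the unadjusted one. The further share explained is f = 1 − (1 − R²full)/(1 − R²planned), and the interval shrinks by 1 − √(1 − f). R² values come from a simulation of 400,000 patients in 11 centres. It had 23.75% mortality, between-centre variation corresponding to a correlation of about 0.02, and a severity score correlated with ventilation, dose and age. The full model adds age, the severity score and continuous dose. Power is Φ(7.5/SE − 1.96) with SE = 2.677 × √(1 − R²).

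| AUC planned → full | R² planned → full | f | Half-width (points) | Narrower by | Power |
|---|---|---|---|---|---|
| 0.587 → 0.629 | 0.018 → 0.038 | 0.021 | 5.20 → 5.15 | 1.1% | 80.7% → 81.5% |
| 0.609 → 0.675 | 0.027 → 0.072 | 0.046 | 5.18 → 5.05 | 2.3% | 81.1% → 82.9% |
| 0.631 → 0.717 | 0.039 → 0.114 | 0.078 | 5.14 → 4.94 | 4.0% | 81.5% → 84.5% |
| 0.652 → 0.757 | 0.053 → 0.162 | 0.115 | 5.11 → 4.80 | 5.9% | 82.1% → 86.4% |
| 0.674 → 0.802 | 0.069 → 0.228 | 0.171 | 5.06 → 4.61 | 8.9% | 82.7% → 89.0% |

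The last four rows are the plausible range: f of about 5–17%, an interval 2–9% narrower, and power 2–6 points higher. The first row shows weak covariates.

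**Step 4: without SAPS II or numeric dose.** Suppose the remaining covariates explain a further 3–5% of variance (assumption). The interval narrows by 1 − √0.97 = 1.5% to 1 − √0.95 = 2.5%. Starting from R² = 0.027 (81.1%), R² becomes 1 − 0.973×0.97 = 0.056 (82.2%) or 1 − 0.973×0.95 = 0.076 (83.0%), a gain of 1–2 points.

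**Step 5: does the gain reach the decision?** The stratified Farrington-Manning test takes strata, not continuous covariates. Changing only the estimation model would leave that test as it is.

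**The case against.** The strongest reply is that nothing here is wrong. The planned interval is valid, the model adjusts for every randomisation factor, and the sample size reaches 80% power with no covariates. This stands: the point concerns efficiency, not an error.

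Four stronger readings are tempting, and the documents do not support them.

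- **Severity and dose are ignored.** They are not. Ventilation and the dose stratum both mark severity and are in the model. Only the information beyond them is lost.
- **Everything needed is already held.** Assigning the stratum requires knowing only which side of 0.18 µg/kg/min the patient falls on, and nothing says that the numeric dose was kept. The timing of SAPS II is not stated, and the same log holds ICU survival, so it is not purely a pre-randomisation record. SOFA is scheduled from Day 1, which starts at randomisation.
- **Power would rise from 81% to 86%, as if 16% more patients had been enrolled.** That figure needs one strong severity covariate (AUC about 0.73) unrelated to ventilation and dose, which gives about 13% less variance. With an assumed correlation of 0.4–0.6 and the same AUC, the further reduction is 9% to 6%.
- **Adjusting the model alone would sharpen the non-inferiority decision.** Step 5 shows that it would not.

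Timing is the remaining objection, and much of it stands. The model was settled during data analysis, after day-28 mortality had been examined by group for within-centre correlation. Changing the primary again could add post hoc flexibility, so the adjusted result may be admissible only as supportive.

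**Conclusion.** The point holds as a modest missed efficiency. The direction is secure: prognostic pre-randomisation covariates should narrow the interval without changing the estimand or the margin. The size is not secure, because covariate strength appears nowhere in the documents. Most of the upper end of the 2–9% range would need a strong severity score whose inputs are known to precede randomisation. The gain would help whatever the true effect, but it does not rescue the zero-difference case. There, power is 45% unadjusted and 80% would need 7.849 × 0.375 / 0.0025 = 1177.3, or 1178 per arm. A benefit to the primary conclusion also requires that the decision rest on the adjusted interval and that outcomes by arm have not been seen.

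**What to change.** In the SAP, Primary outcome:

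1. Keep the day-28 risk difference and the 5-point margin.
2. Fit a logistic working model with arm, ventilation, dose stratum, centre, age and cause of shock as known at randomisation. Standardise over all analysed patients to a marginal risk difference with a robust 95% interval. This also avoids the convergence problems that an identity-link binomial model may have with continuous covariates.
3. Replace the dose stratum with the numeric enrolment dose only if that value was stored before randomisation. Add SAPS II only if all its inputs precede randomisation.
4. Compare the upper bound of the adjusted interval with 5 points, in line with Protocol 6.2, so that estimate and decision agree.
5. Keep the strata-only GEE and the stratified Farrington-Manning test as sensitivity analyses.
6. If outcomes by arm have already been seen, leave the primary unchanged and report the covariate-adjusted result as a labelled supportive analysis.

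The cost is SAP wording and a few lines of code, plus a check of what was stored and when. The small downside is that the covariate list must be short and fixed on prognostic grounds without looking at outcomes.

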Patient-reported pain and discomfort related to the device used for BP monitoring will be measured daily using 4 scales rating from 0 to 10. Each day, a patient will be considered as experiencing pain and/or discomfort if at least one scale is ≥ 4 (Gerbershagen, DOI: 10.1093/bja/aer195). The proportions of patients experiencing at least one day with pain and/or discomfort will be compared with a chi-squared test. The numbers of days with pain and/or discomfort will be compared between the groups with the use of a quasi-Poisson regression model and expressed as rate ratios, with the duration of stay in the ICU as the offset.

- The number of patients reaching the predefined upper limit of vasopressor dosage ($>2.5\mu\text{g}/\text{kg}/\text{min}$ of norepinephrine tartrate plus epinephrine) will be estimated in each group, and day 28 mortality will be described amongst these severely ill patients.

Subgroup analyses

No subgroup analyses were prespecified.

Implementation

Statistician: [name] , Centre d'Investigation Clinique INSERM 1415, CHRU de Tours.

Software: R version 4.3.1

SUMMARY OF CHANGES FROM THE INITIAL PROTOCOL AND JUSTIFICATIONS

Changes in the analyses of the primary outcome

Additional methodological recommendations were identified on current recommendations to estimate a difference in proportions (Pedroza 10.1186/s12874-016-0217-0), recommendations on adjusting stratification variables (Sullivan 10.1002/sim.10060) and recommendations on taking account of the center effect for multicenter studies (Kahan 2013 10.1002/sim.5667, Pedroza 10.1186/s12874-016-0217-0). The final GEE model was established during the analysis of the data, as we observed a significant within-center correlation (Intra-class correlation coefficient = 0.02 for day 28 mortality in each group).

To quantify how strongly our data reject the possibility that the true difference exceeds the 5% noninferiority margin, we employed a stratified Farrington–Manning test. This approach formally tests the noninferiority hypothesis and complements the estimation of the between-group difference obtained with the GEE model. This decision was made during the analysis of the data.

Changes in the analyses of the secondary outcomes

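### Apart from Day-90 mortality, the secondary analyses name no adjustment for randomisation strata or centre, and the six median differences use an unstratified bootstrap, so intervals for differences are probably modestly too wide

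*SAP*

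**What the plan says.** Protocol section 4.1: "Randomisation will be stratified on centres, invasive mechanical ventilation (yes or no) and vasopressor dosage". The SAP's primary analysis is an identity-link binomial GEE model adjusted for the stratification variables and centre. Its summary of changes supports this by citing "recommendations on adjusting stratification variables" and on centre effects, and by reporting an intra-class correlation of 0.02 for day-28 mortality in each group.

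Under the SAP heading for secondary outcomes, 19 outcomes have a stated between-group analysis (ICU and hospital mortality counted as two):

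- Day-90 mortality (1): same model as the primary outcome, so adjusted.
- Death through Day 90 (1): "Cumulative incidence of death from randomization through Day 90 will be analyzed with a Cox model". No covariate or stratum is named.
- ICU and hospital mortality (2): Fine and Gray, none named.
- Durations of ICU stay, hospital stay and ventilation, and three free-day outcomes (6): median differences, with intervals "computed using unstratified bootstrapping (10,000 samples with replacement").
- SOFA (1): linear mixed model with group, time, their interaction and a patient random effect only.
- Renal replacement and vasopressor use (2): difference of proportions, none named.
- Counts (6): quasi-Poisson with ICU stay as offset, none named.

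So 1 of 19 is adjusted, 18 name no adjustment, and 6 use the unstratified bootstrap. The SAP states the bootstrap choice again among its clarifications. It gives no reason for limiting adjustment to mortality at fixed days. It labels secondary findings exploratory.

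**The concern.** Stratified randomisation balances the arms on the strata and so removes between-stratum variation from the treatment comparison. An analysis that ignores the strata still counts that variation in its standard error. For differences in means, medians or proportions, the nominal 95% interval then covers more than 95% and some power is lost.

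This matters mainly because the protocol expects the benefit of the strategy in morbidity rather than mortality (sections 5 and 8), and morbidity sits among these outcomes. Intervals that are too wide can also blur a signal of harm: new renal replacement is an adverse event of special interest in section 15, and renal-replacement use is analysed as a plain difference of proportions. Finally, the SAP's reasons for adjusting the primary outcome apply equally to outcomes from the same randomisation.

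**Working it through.** **Step 1: reproduce the design figure.** The documents give no precision target for secondary outcomes; the only design figure to recompute is the sample size of 1010. Inputs are "the mortality rate at day 28 will be 22.5% in experimental group and 25% in the control group" and "We set the non-inferiority margin at 5%, power at 80% and alpha risk at 5"% (protocol 6.1), 1:1 allocation (section 4), and a primary result "estimated based on the 2-sided 95% Confidence Interval (CI") (6.2), which means one-sided 2.5%.

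n per arm = (1.960 + 0.842)² × (0.225×0.775 + 0.25×0.75) / (0.05 + 0.025)² = 7.849 × 0.361875 / 0.005625 ≈ 505, so N = 1010. This matches exactly. One-sided 5% would give 398 per arm, or 796.

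**Step 2: excess width for a difference.** Let R² be the share of outcome variance explained by the strata and centre. With stratified allocation, the unadjusted standard error is too large by k = 1/√(1−R²). Then:

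- coverage = 2Φ(1.96k) − 1
- power = Φ(2.802 − 1.96k), where adjusted power is 80%
- extra patients to regain 80% power = ((1.96k + 0.842)/2.802)² − 1

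Example, R² = 0.10: k = 1/√0.90 = 1.054; coverage = 2Φ(2.066) − 1 = 96.1%; power = Φ(0.736) = 76.9%; extra patients = (2.908/2.802)² − 1 = 7.7%.

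| R² | Excess width | Coverage | Power | Extra patients |
|---|---|---|---|---|
| 0.02 | 1.0% | 95.2% | 79.4% | 1.4% |
| 0.05 | 2.6% | 95.6% | 78.5% | 3.7% |
| 0.10 | 5.4% | 96.1% | 76.9% | 7.7% |
| 0.20 | 11.8% | 97.2% | 72.9% | 17.2% |

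The first row borrows the stated intra-class correlation for day-28 mortality as the share due to centre. The other rows are assumptions: the documents do not say how prognostic ventilation status or dose stratum is for any outcome.

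**Step 3: check on the bootstrap.** Trials of 1010 patients in 11 centres were simulated with a normal outcome. Blocks of 4 and 50% prevalence of each stratum factor were assumed, and resampling was within arm but not within strata. The ratio of bootstrap to true standard error of the median difference was 1.02 with no stratum effect, 1.03 with centre only (0.02), 1.05 at total R² 0.10 and 1.10 at 0.20. Net of the 1.02 baseline, the excess is about 3% at 0.10 (1.052/1.021) and 8% at 0.20 (1.101/1.021). The direction is confirmed; for medians the size is somewhat below the formula.

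**Step 4: where the formula does not carry over.**

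- SOFA: the group-by-time term is a within-patient contrast, and the patient random effect absorbs level differences between strata. On assumed data (1000 patients, 7 days), adding both stratum factors left its standard error at 0.0239. Only the standard error of the group main effect fell.
- Cox, and Fine and Gray: omitting prognostic factors pulls the hazard ratio towards 1 and yields a marginal rather than a conditional estimand. The standard error of the log hazard ratio need not be larger, so no excess width is claimed.

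**The case against.** The strongest reply is that little is at stake. The secondary findings are exploratory, the error is conservative, false positives are not inflated and the primary analysis is unaffected. Protocol 6.2 named stratum adjustment only for a sensitivity analysis of the primary outcome, so the SAP continues the existing plan for secondary outcomes. Changing many models now, after an amendment that followed the blind review and partly arose during data analysis, adds further post-data choices. All of this stands; it limits the importance of the point and governs how any added analysis must be labelled.

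A reader might also infer more than the documents support:

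- That nearly all secondary analyses use the unstratified bootstrap. It is specified for six median differences only.
- That every secondary interval is too wide. Step 4 shows this is not a general result for hazard ratios or the SOFA interaction.
- That adjusting is worth 5%, 11% or 25% more patients, from 1/(1−R²) − 1 at R² of 0.05, 0.10 and 0.20. Those figures describe equivalent interval width. For power, the equivalents are about 4%, 8% and 17%, because stratified randomisation has already removed the between-stratum variance.
- That the adjusted Day-90 risk difference and the bare Cox model contradict each other. They are different estimands and may use different covariates; what is missing is a reason.

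Adjustment also has limits. Patients in the upper dose stratum receive a vasopressor at enrolment, so their risk of vasopressor use after randomisation is probably near 1, where an identity-link model can fail. Protocol 1.2 cites about 1 related infection per 1000 catheter-days, too few events for many terms.

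**Conclusion.** The omission is real and is not explained: 18 of 19 secondary outcomes with a stated comparison name no stratum or centre term, and six of these use an explicitly unstratified bootstrap. Intervals for differences in medians and proportions, and for the SOFA group main effect, are likely modestly too wide. The documented part, centre alone, is about 1%, and it already assumes that the correlation for day-28 mortality applies to other outcomes. The range of about 3-12%, with power of about 78.5-73% instead of 80%, rests on an assumed 5-20% of variance explained; the simulation suggests somewhat less for medians. Cox and Fine and Gray hazard ratios are marginal and may be attenuated. This is a matter of precision and consistency in exploratory analyses, worth correcting but with no bearing on the non-inferiority conclusion.

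**What to change.** - **Cox, Fine and Gray, SOFA, quasi-Poisson:** add ventilation status and dose stratum, with centre as a stratum, random or clustered effect. For rare counts such as catheter-related bloodstream infections, limit adjustment to what the number of events supports.
- **Proportions:** use the primary GEE model for renal replacement. For vasopressor use, specify a stratum-weighted or standardised risk difference if the identity link fails near the boundary.
- **Median differences:** resample within arm × ventilation × dose stratum (8 cells, about 126 patients each on average). Adding centre would give 88 cells of about 11, for a gain of about 1%. Check outcomes with heavy ties: in a simulation on assumed inputs, stratified resampling for ventilation duration gave standard errors of only 0.87-0.93 of the true value.
- **Labelling:** because the SAP was amended after the blind review, mark these analyses as post hoc and show them beside the specified unadjusted results.

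The stratification factors are known at randomisation, so no new data are needed. The cost is SAP wording, some extra analysis and a longer results table. Adjusted hazard ratios become conditional on the strata and should be described as such.
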